9.3. Serious Adverse Event (SAE) Recording/Reporting

An SAE for this study is one that meets any one of the following criteria:

- Fatal or life-threatening
- Requires or prolongs in-patient hospitalization
- Results in persistent or significant disability/incapacity
- Important medical event

Medical and scientific judgment should be exercised in deciding whether an important medical event is serious. Although the event may not be immediately life threatening, fatal, or result in hospitalization, it should be considered serious when it jeopardizes the patient, or requires an intervention to prevent a serious outcome as defined above. Examples of serious medically important events are: intensive treatment in an emergency room or at home for allergic bronchospasm; blood dyscrasia or convulsion that do not result in hospitalization.

The term "life threatening" in the definition of "serious" refers to an event in which the patient was at risk of death at the time of the event; it does not refer to an event that hypothetically might have caused death if it were more severe. The term "in-patient hospitalization" in the definition of "serious" refers to an event in which the patient was admitted to the hospital for one or more days, even if release on the same day; or an emergency room visit, which results in admission to the hospital. Emergency room visits that do not result in admission to the hospital should be evaluated for one of the other serious outcomes criteria (e.g., important medical event).

The SAE reporting period begins at the time the first Omegaven infusion is administered and ends at the last study visit. SAEs that are considered at least possibly related to the study medication or that occur in a pregnancy that began while the patient was using the study medication can be reported at any time.

All SAEs will be followed through resolution or until the investigator attributes the SAEs to a cause other than the study medication or assesses them as chronic or stable. Follow-up SAE reports should adhere to the same procedures and timelines as initial reports. In addition, any SAE that occurs subsequent to the reporting period that the investigator assesses as possibly related to the study medication should also be considered for follow-up.

9.4. IND Safety Reporting

The Principal-Investigator for this IND shall promptly review all information relevant to the safety of the drug obtained or otherwise received from any source, foreign or domestic, including information derived from any clinical or epidemiological investigations, animal investigations, commercial marketing experience, reports in the scientific literature, and unpublished scientific papers, as well as reports from foreign regulatory authorities that have not already been previously reported to the agency by the Principal-Investigator. The Principal-Investigator of a clinical study of a marketed drug is not required to make a safety report for any AE associated with use of the drug that is not from the clinical study itself.

9.4.1. Written IND Safety Report

The Principal-Investigator shall notify FDA and all participating investigators in a written IND safety report of:

- Any AE associated with the use of the drug that is both serious and unexpected; or
- Any finding from tests in laboratory animals that suggests a significant risk for human subjects including reports of mutagenicity, teratogenicity, or carcinogenicity.

Each notification shall be made as soon as possible and in no event later than 15 calendar days after the Principal-Investigator's initial receipt of the information. Each written notification may be submitted on FDA Form 3500A or in a narrative format. In each written IND safety report, the Principal-Investigator shall identify all safety reports previously filed with the IND concerning a similar AE, and shall analyze the significance of the AE in light of the previous, similar reports.

Follow-up information to an IND Safety Report shall be submitted as soon as the relevant information is available. If the results of the Principal-Investigator's follow-up investigation show that an AE that was initially determined to not require a written IND Safety Report does, in fact, meet the requirements for reporting; Principal-Investigator will submit a written IND Safety Report as soon as possible, but in no event later than 15 calendar days, after the determination was made. Additional safety information shall be submitted, as appropriate, in an information amendment or annual report.

9.4.2. Telephone or Fax IND Safety Reports

The sponsor shall also notify FDA by telephone or by fax of any unexpected fatal or life-threatening experience associated with the use of the drug as soon as possible but in no event later than 7 calendar days after the Principal-Investigator's initial receipt of the information.

9.5. IRB Safety Reporting

Adverse event submissions to the Institutional Review Board (IRB) responsible for this study will follow the responsible IRB's requirements.

10. DATA MANAGEMENT

10.1. Data Management

All patient study files will be centralized with the Principal-Investigator.

10.2. Sample Size Determination

This is a compassionate use study that is expected to enroll 30 patients.

10.3. Disposition and Baseline Assessment

In the event that a patient withdraws prematurely from the study, the reasons for withdrawal will be documented in the patient's study file. Patients who discontinue study medication or withdraw prematurely from the study will be summarized, together with the reason(s) for discontinuation.

10.4. Outcomes Analysis

This is a compassionate use study, with no comparator; therefore the endpoints will be descriptively summarized (continuous data will be presented as mean, standard deviation, median, minimum and maximum; categorical data will be presented as number and percentage). All patients who receive any amount of study medication will be analyzed. The outcome evaluations will include:

- Laboratory results Laboratory values will be summarized at baseline and as change from baseline to worst follow-up values.
- AEs reported by the patient and/or identified by study personnel AEs may be categorized into common terms and summarized as incidence and event rates. If there is sufficient data the incidence rates may also be summarized by AE severity and relationship to study medication.
- **Resolution of hepatic injury** Resolution of hepatic injury will be summarized as incidence and if there is sufficient data may also be presented as time to resolution.
- **Days of PN** Days of PN will be summarized.

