Omegaven will be co-infused via y-site. Containers will be changed every 12 hours. Omegaven will be given through a 1.2 micron inline filter.

Omegaven will be given daily for:

- Up to 4 weeks, or
- Until normalization of alkaline phosphatase, AST, & ALT

The patient may receive other lipids to meet essential fatty acid (EFA) and/or additional calorie needs.

EFFICACY OUTCOME VARIABLES:

- Maximum conjugated bilirubin
- Time to resolution of bilirubin or death
- Average improvement in bilirubin, alkaline phosphatase, AST, & ALT

SAFETY OUTCOME VARIABLES:

- Summary of laboratory results
- Summary of AEs for each patient

			Table of Contents	
1.	LIST OF ABBREVIATIONS AND DEFINITIONS OF TERMS			6
2.		INTRO	DUCTION	7
	2.1.	Backgrou	nd	7
	2.2.	Risk Cate	gory	8
	2.3.	Rationale)	8
	2.4.	Statemer	nt	8
3.		OBJEC	ΓΙVES	8
4.		INVEST	IGATONAL PLAN	9
	4.1.	Study De	sign	9
	4.2.	Study Pro	ocedures by Visit	10
		4.2.1. S	creening Visit	10
		4.2.2. C	Day 1 Visit	10
		4.2.3. E	Day 2/Day 3 Visit	10
		4.2.4. C	Day 5 Visit	10
		4.2.5. V	Neekly Visits During Home Use of Omegaven (up to 4 weeks of treatment)	11
		4.2.6. F	inal Study Visit/Early Withdrawal Visit	11
	4.3.	Description	on of Study-Specific Procedures	11
		4.3.1. C	Diagnostic Tests	11
5.		SELECT	ION AND WITHDRAWAL OF PATIENTS	12
	5.1.	Patient Ir	clusion Criteria	12
	5.2.	Patient E	xclusion Criteria	12
	5.3.	Patient W	/ithdrawal Criteria	12
6.		CONCO	OMITANT MEDICATIONS/TREATMENT	13
7.		COMPI	LIANCE	13
8.		INVEST	IGATIONAL MATERIALS AND MANAGEMENT	13
	8.1.	Investiga	tional Product	13
		8.1.1. 0	General Investigational Product Information	13
		8.1.2. C	Dosing	14
		8.1.3. C	Dispensation	14
		8.1.4. 5	torage and Handling	14
		8.1.5. A	Accountability	14
		8.1.6. C	Dose Adjustments	14
9.		ASSESS	MENT OF EFFICACY AND SAFETY	14
	9.1.	Outcome	Variables	14
	9.2.	Adverse I	Event (AE) Recording/Reporting	14
	9.3.	Serious A	dverse Event (SAE) Recording/Reporting	16
	9.4.	IND Safet	y Reporting	16
		9.4.1. V	Vritten IND Safety Report	17
		9.4.2. T	elephone or Fax IND Safety Reports	17
	9.5.	IRB Safet	y Reporting	17
10.		DATA I	MANAGEMENT	17
	10.1.	Data Mar	nagement	17
	10.2.	Sample S	ize Determination	17
	10.3.	Dispositio	on and Baseline Assessment	17
	10.4.	Outcome	s Analysis	17
	10.5.	Data Mor	nitoring Committee	18
	10.6.	Study Ter	mination	18

	10.7.	Study Medication Administration	. 18
	10.8.	Concomitant Medications	. 18
11.		STUDY ADMINISTRATION	. 18
	11.1.	Adherence to the Protocol	. 18
	11.2.	Amending the Protocol	. 19

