3. OBJECTIVES

The primary objective for this study is to examine if an omega-3 based lipid emulsion (Omegaven) can improve or prevent further deterioration of PN induced hepatic dysfunction.

The secondary objective for this study is to examine the effect of an omega-3 based lipid emulsion (Omegaven) on immune function and markers of the inflammatory process.

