8.1.2. Dosing

Patients will be treated with Omegaven on day 1 at a dose of 0.1 g/kg body weight (1 ml/kg). On day 2 or 3, it will be increased to 0.2 g/kg body weight (2 ml/kg). For patients > 120% ideal body weight, adjusted body weight will be used for dosing. The infusion rate will not exceed 0.5 ml Omegaven/kg body weight/hr = 0.05 g fish oil/kg body weight/hr.

Omegaven will be co-infused via a y-site. Containers will be changed every 12 hours. Omegaven will be given through a 1.2 micron inline filter.

Omegaven will be given for:

- 4 weeks, or
- Until serum bilirubin is < 2 mg/dL, or
- Until normalization of liver function tests.

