9. ASSESSMENT OF EFFICACY AND SAFETY

9.1. Outcome Variables

Efficacy and safety will be assessed using the following outcome variables:

- Laboratory results
- AEs reported by the patient and/or identified by study personnel
- Resolution of hepatic injury

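### Section 10.4 summarises follow-up laboratory values only as change to the worst value, which does not give the average improvement that the synopsis names as an efficacy outcome

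*Protocol*

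**What the plan says.** The primary objective in section 3 is to examine whether Omegaven "can improve or prevent further deterioration of PN induced hepatic dysfunction". The synopsis lists three efficacy outcomes: "Maximum conjugated bilirubin", time to resolution of bilirubin or death, and "Average improvement in bilirubin, alkaline phosphatase, AST, & ALT". Among the safety outcomes it lists "Summary of laboratory results".

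Section 9.1 merges the two roles. Under the lead-in "Efficacy and safety will be assessed using the following outcome variables" it names laboratory results, adverse events and resolution of hepatic injury.

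Section 10.4 follows that list. It gives the descriptive statistics for continuous data (mean, standard deviation, median, minimum, maximum) and then says for laboratory results: "Laboratory values will be summarized at baseline and as change from baseline to worst follow-up values". Its other efficacy summary is "Resolution of hepatic injury will be summarized as incidence", with time to resolution if the data allow. It does not say which visits count as follow-up.

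**The concern.** The objective has two halves, improvement and prevention of deterioration. Change to the worst value speaks to the second half. It does not measure the first, although improvement in four liver tests is a named efficacy outcome.

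The distortion has a predictable direction, for two reasons. Chemistry is drawn on Days 2 and 3 (sections 4.2.3 and 4.2.4), when even a good responder is still near baseline, so those draws tend to supply the worst value. And the maximum of several noisy measurements is set against a single noisy baseline, which pushes the summary upward even when nothing has changed.

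At stake is how a partial response would appear in about 30 patients. Followed as written, 10.4 reports full resolution and worst deterioration. A real improvement short of resolution could be tabulated as no change or slight worsening.

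**Working it through.** The protocol gives no effect size, standard deviation or derivation of the sample size, so there is no figure to reproduce. The mismatch comes from the text; the arithmetic only illustrates its size.

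**Inputs from the protocol.** Chemistry at Days 2 and 3 and weekly for up to four weeks, that is 1, 2, 7, 14, 21 and 28 days after the first dose. Bilirubin target below 2 mg/dL (synopsis, sections 4.2.5 and 8.1.2).

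**Assumptions.** Baseline bilirubin 3.5 mg/dL; linear fall to week 4; independent log-normal error with CV 10% to 25% on every value; no early stopping. Two readings of follow-up: (a) Days 2 and 3 plus weeks 1 to 4, six draws; (b) weekly draws only, four draws.

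**No noise, true fall of 30%.** The true week 4 change is -0.30 × 3.5 = -1.05 mg/dL. The worst value is the first draw:
- (a) -3.5 × 0.30 × 1/28 = -0.04 mg/dL
- (b) -3.5 × 0.30 × 7/28 = -0.26 mg/dL

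**Noise, no true change.** Baseline and follow-up draws are exchangeable, so the worst follow-up value exceeds baseline with probability 6/7 = 86% under (a) and 4/5 = 80% under (b), whatever the CV. The expected maximum of six normal values is 1.267 SD above the mean, and of four 1.029 SD. At CV 10% the SD is 0.35 mg/dL, giving about +0.44 and +0.36; simulation with log-normal error gives +0.46 and +0.37.

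**Simulation, 400,000 patients per scenario; ranges run from CV 10% to CV 25%.**

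| True change at week 4 | Mean change to worst, (a) | Look worse, (a) | Mean change to worst, (b) | Look worse, (b) |
|---|---|---|---|---|
| 0 | +0.46 to +1.20 | 86% | +0.37 to +0.94 | 80% |
| -1.05 (30%) | +0.19 to +0.74 | about 67% to 75% | -0.18 to +0.20 | about 35% to 59% |
| -1.75 (50%) | +0.12 to +0.57 | not tabulated | -0.41 to -0.18 | not tabulated |

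Change to the week 4 value returns -1.05 mg/dL for the 30% fall, with 85% to 99% of patients at or below baseline (50% when stable).

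**A second model agrees.** With a log-linear fall, six follow-up draws and CV 10%, a true 50% fall gives a mean change to worst of +3.3%, against +14.3% with no change. In 93% of those improving patients the worst value is on Day 2 or 3. So the summary moves a little with improvement but does not estimate it.

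**Does resolution fill the gap?** If resolution means bilirubin below 2 mg/dL, a patient starting at 3.5 must fall by more than (3.5 - 2)/3.5 = 43%. A true fall to 3.5 - 1.05 = 2.45 mg/dL is not resolution, and the worst-value summary largely hides it as well.

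**The case against.** The strongest reply is that 10.4 opens by saying endpoints will be summarised with means and other statistics, and that its list is introduced as what evaluations will include, which is not exhaustive. On that reading average improvement is covered and only its time point is left to a SAP. This fails because the general sentence names statistics, not the follow-up value. The laboratory bullet does fix that value, and the one it fixes does not deliver the named outcome. A SAP that follows 10.4 would carry the mismatch forward.

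A second reply is that the worst value has proper uses: maximum conjugated bilirubin, laboratory safety, and the deterioration half of the objective. That stands, and it is why the worst-value summary should be kept.

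A third concerns the figures, and much of it stands:
- At CV 25%, 41% of patients with a true 30% fall have at least one weekly value below 2 mg/dL and 24% are below 2 at week 4, so some could be counted as resolved. At CV 10% the share is about 2%.
- At CV 5% with weekly draws only, the 30% fall reads -0.25 mg/dL and 14% look worse, so apparent worsening needs either the Day 2 and 3 draws or more noise.
- Only bilirubin is modelled, although patients may enter on ALP, AST or ALT, and stopping at target is left out.

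Finally, nothing is lost irreversibly. The study is uncontrolled and descriptive, and the missing summary could be produced at analysis.

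**Conclusion.** The concern holds. The one follow-up laboratory summary that section 10.4 states does not yield an efficacy outcome that the synopsis names, and it largely hides improvement short of resolution. This rests on the text alone.

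The size is illustrative and depends on the assumed baseline, trajectory and noise, and on which visits count as follow-up. Even under the kinder reading (weekly draws, CV 10%), a true change of -1.05 mg/dL is reported as -0.18, so about 83% of it disappears (1 - 0.18/1.05). The finding that 80% to 86% of stable patients look worse needs only exchangeable draws.

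The protocol should be corrected on this point. It does not undermine the resolution or safety summaries.

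**What to change.** In section 10.4, for bilirubin, ALP, AST and ALT:
- Define baseline as the last value before the first infusion (screening or Day 1).
- Summarise change from baseline to each weekly visit and to the final or early withdrawal visit, with the number and percentage at or below baseline at the end. State that this is the analysis of the synopsis's average-improvement outcome.
- Keep change to the worst value for safety and deterioration, and say which visits count as follow-up.
- Give the number still on treatment at each visit, and state beside the tables that without a comparator the change cannot be attributed to treatment.

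The cost is a few sentences and tables, since the panel is already drawn at every visit including early withdrawal.

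The final-visit change has its own bias, which should be stated. Final values fall at different times, patients enter on high values, and treatment stops when the tests reach target. All of this is uncontrolled. For example, take stable patients with a true bilirubin of 2.5 mg/dL who enter on a value above 2 and up to 5, with the last value taken at the first weekly value below 2, or at week 4 if there is none. Their mean final change is -0.03 mg/dL at CV 10% and -0.59 at CV 25%, although nothing changed. At week 4 without stopping it is -0.01 and -0.20. At a true level of 3.5 mg/dL the final change is 0.00 and +0.02. The by-visit tables must therefore stand beside the final-visit table.

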10.5. Data Monitoring Committee

No plans for a Data Monitoring Committee (DMC).

10.6. Study Termination

This is a compassionate use study, intended to make a study medication available to patients who would otherwise not be able to receive this medication, therefore there is no predefined completion of this study. When the study is terminated for any reason, the patients will be treated as deemed appropriate by their usual healthcare provider. Some of the possible reasons for study termination are patient safety, Principal-Investigator termination of the study, etc.

Safety will be monitored throughout the study and if a safety concern indicative of a risk for the individual patients or the study population is identified at any time during the study, this will warrant further review and may result in the termination of the study.

10.7. Study Medication Administration

Study medication administration will be summarized. Any deviation from the planned dosing schedule will be documented and summarized.

10.8. Concomitant Medications

Concomitant medications are the medications that are taken during the study. Information on the concomitant medications will be collected in the patient's study file.

11. STUDY ADMINISTRATION

11.1. Adherence to the Protocol

Except for changes that are intended to eliminate an immediate hazard to patients, the approved protocol shall be conducted as described. Any protocol deviation or violation must be documented. Any protocol-related issue that poses an immediate or significant hazard to patients must be reported to the IRB immediately.

The Principal-Investigator may not implement any deviation or change to the protocol without prior review/favorable opinion of the appropriate regulatory authorities (e.g., IRB), except where necessary to eliminate an immediate hazard to a patient or when the change involves only a logistical or administrative aspect of the study (e.g., change of telephone numbers, ancillary personnel). Any deviation from the protocol must be documented and explained in written communication to the appropriate regulatory authorities.

This clinical study will be conducted in compliance with the protocol, Good Clinical Practices (GCPs), and the applicable regulatory requirements. Where applicable, the protocol designates study responsibilities to the "Investigator". Those tasks may be performed by the Principal Investigator or qualified designee.

11.2. Amending the Protocol

Any change to the protocol, once the final version has been issued, has to be detailed in a protocol amendment. All protocol modifications and amendments must be prepared for and approved by the IRB. All amendments must be numbered, dated and signed. Amendments cannot be implemented until final approval from the IRB.

11.3. Direct Access to Source Data/Documents

All representatives of the Principal-Investigator with direct access to patients' medical records will take reasonable precautions within the constraints of applicable regulatory requirements to maintain the confidentiality of the patients' identity. Auditors of the IRB and government inspectors may evaluate the study and must be allowed access to the patient study files, source documents and other study files. Audit reports will be kept confidential.

11.4. Quality Control and Quality Assurance

Quality assurance measurements are designed to ensure that complete, timely and accurate data are submitted, that protocol requirements are followed, and that complications and/or AEs are immediately identified. Quality assurance audits may be carried out during the conduct of the study. Quality assurance personnel independent of personnel conducting the study will carry out these audits. The quality assurance auditor should have access to all medical records, the Principal-Investigator's study-related files and correspondence, and the informed consent documentation that is relevant to this clinical study.

11.5. Data Monitoring Committee (DMC)

No plans for a DMC.

11.6. Ethical Considerations and Patient's Consent

11.6.1. Ethical Considerations

The study will be carried out in accordance with the principles stated in the Declaration of Helsinki and in accordance with Good Clinical Practice (GCP) and applicable regulatory requirements.

11.6.2. Institutional Review Board (IRB)

According to the applicable regulatory requirements, the investigator will submit the study documentation to the relevant IRBs. The letter of approval from the IRB (or a copy), which contains a list of the names and occupations of the members of the IRB having participated at the session, as well as a list of submitted documents, must be received by the Principal-Investigator prior to study medication being received at the study site. Patients must not be entered into the study until approval of the IRB(s) as defined by local regulatory requirements. All subsequent substantial amendments must be submitted to the IRB(s) for approval/information.

11.6.3. Written Informed Consent

A patient may be included in this study only after an IRB-approved Informed Consent Form (ICF) has been signed and dated by the patient. The patient must be informed about the content of the planned

study as well as on the benefit/risk ratio. The person who conducts the informed consent discussion at the study site will also be required to sign and date the ICF.

